The study will be performed at the Baylor College of Medicine. Approval from Site Review Authority will be obtained. Subjects will be recruited from outpatient clinics at Baylor College of Medicine.

We propose a randomized crossover trial (Phase I/II) to evaluate acceptability as well as short (1 week) and intermediate (6 week) benefits and effectiveness of Orthofeet in reducing foot pain, increasing daily physical activities, and improving functional performance in ambulatory patients suffering from foot pain.

We are proposing a clinical study at the Baylor College of Medicine, to evaluate short and intermediate benefits and effectiveness of a novel pain relief footwear, called Orthofeet. This is a randomized crossed over trial. The duration of the study would be 12-week. We will recruit 50 eligible ambulatory adults (age 50 years or older) with moderate to severe self-reported foot pain. Participants will be randomly assigned to Group A (25 subjects) and Group B (25 subjects). There is no difference in assessments or eligibility between Group A and Group B, the only difference is when they have the opportunity to try the shoes for 6 weeks. Group A will receive a pair of Orthofeet shoes with adjustable insoles and will be asked to wear it every day activities of daily living for duration of six weeks. Participants will be also encouraged to wear the shoes inside of home if possible. Group B will be followed for duration of six weeks. At six weeks the groups will be switched and group B will receive a pair of Orthofeet shoes with adjustable insoles and Group B will follow-up for six weeks without Orthofeet shoes. Participants will be assessed at baseline, week-1, week-6, week 7, and week 12.

The primary outcome includes changes compared to baseline in foot pain intensity.

The secondary outcomes includes changes compared to baseline in various metrics of daily physical activities (e.g., daily step, longest walking bout, cadence, standing duration, and standing duration).

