At Visit 3 (6 Week Follow Up) the participant will complete all the same assessments and questionnaires as baseline. At this visit, Group A will stop wearing OrthoFet shoes and continue the study without them. Group B will be supplied with OrthoFet shoes to wear for the rest of their study participation until 12 Week Follow Up.

At Visit 4 (7 Week Follow Up) the participant is called by the research staff to complete the pain questionnaire, document adverse events, and answer any study-related questions.

At Visit 5 (12 Week Follow Up) the participant will complete all the same assessments and questionnaires as baseline. All participants will return OrthoFeet shoes by this point.

Section G: Sample Size/Data Analysis

G1. Sample Size

How many subjects (or specimens, or charts) will be used in this study?

Local: 50 Worldwide: 50

Please indicate why you chose the sample size proposed:

This is a proof of concept study. The sample size is 50 eligible participating in a randomized crossover study. The sample size is convenient and is selected to detect a between group difference for the primary outcome (change in foot pain) with medium effect size (Cohen's $d=0.50$) with a dropout rate of 15%, alpha of 5%, and power of 80%. The anticipated effect size was estimated from our prior study (Najafi et al, Journal of Foot and Ankle Research, 2014) in which we observed a significant drop in foot pain after orthotic therapy compared to sham orthotics. Based on this pilot study, we will propose a Phase II study to validate the observed effect in the follow-up study.

G2. Data Analysis

Provide a description of your plan for data analysis. State the types of comparisons you plan (e.g. comparison of means, comparison of proportions, regressions, analysis of variance). Which is the PRIMARY comparison/analysis? How will the analyses proposed relate to the primary purposes of your study?

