Who will recruit subjects for this study?

PI

PI's staff

Describe how research population will be identified, recruitment procedures, any waiting period between informing the prospective participant and obtaining consent, steps taken to minimize the possibility of coercion or undue influence and consent procedures in detail.

Participants will be recruited based on referral from their clinician or through recruitment flyers placed in Baylor Clinic. The eligible subject will contact us or be approached by the research personnel after being referred by the clinical physician and his clinical staff (part of the research team). The subject will be fully informed about the study, and should voluntarily agree to participate with the guidelines as stipulated in the informed consent. The study coordinator or designee will introduce the study, present the written consent form, and spend as much time as necessary to ensure the potential subject completely understands the protocol. Emphasis will be placed on the voluntary nature of participation and the subject will be assured that his/her care will not be compromised in any way whether or not they choose to participate. The subject will be informed s/he can withdraw from the study at any time without loss of benefits. Consent forms will then be signed and dated by the subject and individual obtaining consent (PI, co-PI, study coordinator, or designee). Once written consent is obtained, the protocol may begin immediately or a follow-up appointment may be made. The individual (PI, co-PI, study coordinator, or designee & interns) obtaining consent will be given a thorough training of the process and go through several mock consent scenarios. The consent training consists of understanding the study and being able to fully explain it to the participant providing all pertinent information (procedures, risks, benefits, alternatives to participant), giving sufficient time to the participant to consider whether or not they would like to participate, and answer any questions which the subject may have. The training will have a strong emphasis on subject comprehension of the research study by asking open-ended questions to the subject.

The original documents (with signature) will be maintained per IRB policy. Any critical information will be sent for inclusion

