Discuss the potential for psychological, social, and/or physical harm subsequent to participation in this research. Please discuss, considering the following areas: risks to privacy, confidentiality, insurability, employability, immigration status, paternity status, educational opportunities, or social stigma.

Will subjects be offered any type of genetic education or counseling, and if so, who will provide the education or counseling and under what conditions will it be provided? If there is the possibility that a family's pedigree will be presented or published, please describe how you will protect family member's confidentiality?

Section N: Sample Collection

None

Section O: Drug Studies

Does the research involve the use of ANY drug* or biologic? (*A drug is defined as any substance that is used to elicit a pharmacologic or physiologic response whether it is for treatment or diagnostic purposes)

No

Does the research involve the use of ANY gene transfer agent for human gene transfer research?

No

O1. Current Drugs

Is this study placebo-controlled?

No

Will the research involve a radioactive drug?

No

Section P: Device Studies

Does this research study involve the use of ANY device?

Yes

[Device 1: Legsys](#)

[Device 2: Kent Camera](#)

[Device 3: Frailty Meter](#)

[Device 4: Balansens](#)

[Device 5: Pamsys](#)

[Device 6: OrthoFeet Shoes](#)

[Section Q: Consent Form\(s\)](#)

A PROSPECTIVE PROOF OF CONCEPT TRIAL TO EVALUATE EFFICACY, ACCEPTABILITY, AND PERCEPTION OF BENEFIT OF AN INNOVATIVE PAIN RELIEF FOOTWEAR -ORTHOFEET

Section R: Advertisements**Mode of Advertising: Bulletin Board**

Exact language of Advertisement:

Foot Pain Research Trial What have you tried to manage foot pain? Do you experience mild to severe foot pain? Would you want to try on new shoes meant for relief for 6 weeks? If you answer yes to the following questions, you may qualify for our clinical trial with OrthoFeet shoes! Benefits of participation include Help to advance scientific knowledge about foot pain Use new shoes for foot pain relief! You will receive compensation for your time For more information, please contact our research coordinators. [name] [contact] [contact] [name] [contact] [contact]

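### The flyer and the title listed for the consent form present pain relief as a benefit in an unmasked shoe versus no-shoe trial with self-reported pain as primary outcome; neutral wording is a cheap improvement

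*Combined protocol and SAP*

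**What the plan says.** Section R gives the exact flyer text. It asks "Would you want to try on new shoes meant for relief for 6 weeks" and, under the benefits of participation, lists "Use new shoes for foot pain relief". The title under Section Q, Consent Form(s), ends "PERCEPTION OF BENEFIT OF AN INNOVATIVE PAIN RELIEF FOOTWEAR -ORTHOFEET".

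F1 sets the comparator. In the first period "Group B will be followed for duration of six weeks" without the shoes, and between the two groups "the only difference is when they have the opportunity to try the shoes for 6 weeks". No sham shoe, participant masking, blinded assessor or expectancy rating is described. The form answers No to "Is this study placebo-controlled", although that item sits under the drug-study questions and is weak evidence about a device trial.

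The primary outcome in F1 is change from baseline in foot pain intensity. F2 measures foot pain with the Foot Function Index, which participants complete themselves; at weeks 1 and 7 research staff collect the pain questionnaire by telephone. Acceptability and perceived benefit are also self-reported.

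J2 gives two routes into the trial: "Participants will be recruited based on referral from their clinician or through recruitment flyers placed in Baylor Clinic".

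**The concern.** Participants know in each period whether they have the shoes, and they score their own pain. If they expect relief, the expectation acts on the readings taken while wearing the shoes, and disappointment may act on the readings taken without them. The crossover does not cancel this. Crossing over balances effects tied to calendar period, but expectation follows the shoe in both sequences and so adds to the treatment contrast.

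Recruitment text that offers relief as a reason to join can raise that expectation and can attract people who already hold it. What is at stake is how a positive result is read: part of an observed drop in pain, and of the perceived-benefit scores, could reflect the message and not the footwear. G1 says that the pilot will lead to a Phase II proposal to validate the observed effect, so an inflated estimate would carry forward.

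**Working it through.** **1. Participant-facing text against the protocol's own position.**
- Section D treats pain reduction as a hypothesis.
- Section I, asked what the individual subject gains, says only that the effect on foot pain will be characterised. It promises no relief.
- The flyer lists relief as a benefit. It does not say that the effect is unknown, and it does not mention the six weeks without shoes.

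The flyer therefore goes further than the protocol.

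**2. Does the design absorb expectation?** The comparator is no shoe, nothing is masked and the primary outcome is self-rated, so it does not. Section C itself warns that self-reported health and function questionnaires are open to bias. The effect size in G1 is drawn from a study in which "we observed a significant drop in foot pain after orthotic therapy compared to sham orthotics"; this trial has no such control.

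**3. How much could expectation matter?** The documents give no figure for expectation, so the shift *b* below is an assumption. The sample size serves only to set the number of completers: 50 × (1 − 0.15) = 42.5, taken as 42, or 21 per group. (The 50 in G1 does not follow from its stated inputs under a paired t-test, which needs 34 completers or 40 enrolled, nor under a two-group test, which needs 126 completers or 149 enrolled. That is a separate matter and nothing here depends on it.)

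G2 names no primary test, so two are shown. Both assume a shoe with no true effect and a two-sided 5% level.

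- *Paired test, 42 completers, b in SDs of the within-person difference.* Rejection probability = 1 − F(t*) + F(−t*), where F is the noncentral t distribution with 41 degrees of freedom and noncentrality b√42, and t* is the two-sided 5% critical value.
- *Two groups of 21, b in between-person SDs, normal approximation.* Rejection probability = Φ(b/√(2/21) − 1.96) + Φ(−b/√(2/21) − 1.96).

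| Assumed total expectation shift b | Paired, n = 42 | Two groups of 21 |
|---|---|---|
| 0 | 5% | 5% |
| 0.1 | 10% | 6% |
| 0.2 | 24% | 10% |
| 0.3 | 48% | 16% |

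The two columns use different SD scales and are not like for like. The entries count rejections in either direction.

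**4. What the table does and does not measure.** It shows the effect of *total* expectation under an assumed test. Total expectation is what the unmasked design produces plus whatever the wording adds. Neutral wording can change only the second part, and the documents give nothing from which to estimate it.

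**The case against.** The strongest reply is that the bias belongs to the design. Anyone given shoes in a foot-pain study can infer what they are for, and neutral text would leave the comparison unmasked. This stands: a reader might infer that the recruitment text creates the bias, and the documents do not support that.

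A reader might also infer that participants are told the shoe works. That is too strong. The flyer's phrases state an intended purpose, the flyer calls itself a research trial and speaks of advancing knowledge, and the full title says that efficacy is to be evaluated. What remains is that relief is listed under benefits of participation.

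Exposure is partial. Patients referred by a clinician may never see the flyer, and J2 requires that every subject be fully informed. The body of the consent form is not available, so it may already say that benefit is uncertain. The title, however, is listed for the consent form.

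The sham comparison in G1 is described in one clause. That expectation was balanced in that study is an inference that cannot be checked here.

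Finally, this is a pilot, and the sensor-based activity, gait and balance measures are less exposed to expectation. That is fair, but none of them is the primary outcome.

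**Conclusion.** The point holds as a modest one. The wording may add, by an unknown amount, to an expectation bias that comes mainly from the unmasked comparison with no shoe. That the trial is open to the participant is inferred from the absence of any described masking; the documents do not use the term.

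The size attributable to the wording cannot be given, and it could be close to zero. A reader might take the 10%, 24% and 48% in the paired column as false-positive rates caused by the flyer. They are not: they describe an assumed total expectation effect under a test that the plan does not name, and with two groups of 21 the corresponding figures are 6%, 10% and 16% on another scale. They show only that a small total shift can matter.

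The change is worth making because it is specific, costs little and brings the flyer into line with the protocol's own statement of benefit. It does not by itself decide whether the trial can answer its question.

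**What to change.** - **Flyer (Section R).** Delete "Use new shoes for foot pain relief" and take the reference to relief out of "Would you want to try on new shoes meant for relief for 6 weeks". Say that benefit is unknown and describe both periods, for example: *We are studying whether a type of shoe changes foot pain; it is not known whether it helps. You will use the study shoes for six weeks and go without them for six weeks.*
- **Participant-facing title (Section Q).** Drop the three words that describe the footwear as innovative and pain-relieving, leaving the product name. Check the consent form's body for the same wording.
- **Data analysis (G2).** F1 already defines the comparator. Add to G2 that the primary contrast is Orthofeet versus no Orthofeet, unmasked, and that any difference includes expectation effects.

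The cost is an IRB wording amendment and possibly slower recruitment. Sample size, visits and procedures do not change. Neutral wording lowers expectation but does not remove it, which is why the statement in G2 is needed as well.
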